9.2 Phase II Endpoints

9.2.1 Sample Size of Phase II

The sample size estimate for phase II is based upon a two-stage Simon's optimal design. The primary efficacy endpoint will be the objective response rate (partial or complete response). A Simon (1989), optimum two-stage design will be employed. A 19% response rate precludes further study whereas a 39% response rate would indicate that further investigation of the treatment is warranted (i.e., $P_0=0.19$ and $P_1=0.39$ in the Simon terminology). Using α and β errors of 0.10 and 0.20, respectively, 11 patients will be enrolled in the first stage and this will include the 6 patients in the PK cohort. If 2 or fewer responses are observed, the trial will be terminated. Otherwise, an additional 16 patients will be enrolled in the second stage and if ≤ 7 responses are observed among the 27 patients, the agents will not be considered worthy of further testing; whereas, if 8 or more responses are observed the drugs will be

considered sufficiently active to justify further study. This design has 80% power under the alternative hypothesis and provides a 65% probability of early stopping if the true response rate is only 19%. Therefore, a maximum of 27 patients will be accrued to the phase II portion of the study.

9.2.2 Response Rate Statistics

Radiological response will be analyzed using an intent-to-treat approach of including all enrolled patients. After every 2 cycles of protocol therapy, patients will undergo imaging studies to assess for response to therapy using RECIST. At study termination, each patient's case will be reviewed to determine a best overall response to therapy by RECIST. A descriptive analysis of evidence of antitumor activity will be provided based on radiographic assessments of activity. The proportion with PFS at 6 months will also be calculated based on RECIST criteria.

9.2.3 Toxicity Profile Statistics

Safety will be assessed through a summary of adverse events and laboratory test results. Safety analyses will include all patients who receive at least one dose of study regimen. Verbatim description of treatment-related adverse events will be mapped to thesaurus terms. Adverse events assessed as related to study drug and serious adverse events will be summarized similarly. Adverse events leading to treatment discontinuation will also be summarized. The safety analysis will include a tabulation of all toxicities by grade. The frequency of toxicities will be tabulated separately for each treatment dose level. Treatment safety and toxicity will be evaluated using NCI CTCAE v 4.03 with scheduled assessments every week for the first cycle and then biweekly thereafter.

9.3 Exploratory Endpoints

Exploratory endpoints in this phase I/II trial will be assessed in all patients enrolled in the phase II portion of this study. As noted above, patients who are removed from study for reasons other than disease progression (i.e. for toxicity or patient preference) will be censored for measurement of secondary endpoint, PFS at 6 months, at the time of their latest objective tumor assessment. Exploratory endpoints include:

- Correlate the expression of tissue MGMT as measured by IHC with PFS.

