2.2.2 Phase II Secondary Objectives

2.2.2.1 Determine PFS and OS, disease control rate (DCR), and duration of response (DOR).

2.2.2.2 Determine the safety and toxicity profile of the combination in a larger cohort of patients.

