5.9 Follow-Up

After treatment discontinuation, patients will be followed every 6 months for 1 year in clinic and/or via phone for survival follow-up. The study will end 30 days after the last patient discontinues therapy and completes the protocol-defined follow-up period.

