6.2.2 Secondary Endpoints

6.2.2.1 Determine PFS, OS, DCR, and DOR.

For these endpoints, all enrolled patients will undergo contrast-enhanced CT or MRI imaging at baseline and after every 2 cycles of protocol therapy until study discontinuation. Please see Section 6.3 for definitions.

6.2.2.1.1 PFS will be defined as the time from the first study treatment to the first occurrence of progression or death.

6.2.2.1.2 OS will be defined as the time from first study treatment until death from any cause.

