⁷ Imaging with CT or MRI (whichever test is used for a particular patient at baseline should be the same that is used throughout for disease assessment). Response will be assessed every 2 cycles (8 weeks +/- 7 days). After 1 year of protocol therapy, patients may switch to imaging every 12 weeks (+/- 7 days) per treating physician's discretion.

⁸ Temozolamide will be administered on Days 1-7(+/-1 day) and 15-21(+/-1 day) of each cycle. Please refer to Section 5.2 for further details.

⁹ Pazopanib will be administered continuously starting Cycle 1, Day 1 until study discontinuation. Please refer to Section 5.2 for further details.

¹⁰ All patients will receive prophylaxis with trimethoprim-sulfamethaxazole double strength (sulfamethoxazole 800 mg and trimethoprim 160 mg) by mouth 3 times a week.

¹¹ Patients will continue on treatment until disease progression (or until removed from study for other reasons, as outlined in Section 5.8.1).

¹² Patients removed from the study for disease progression who have no ongoing toxicity will undergo one last off-treatment visit for response. Survival follow-up will continue every 6 months for 1 year in clinic and/or via phone ; survival follow-up may occur either in clinic or via phone contact. Additional follow-up may be required for patients experiencing toxicity at the time of treatment discontinuation.

¹³ Patients in the PK cohort only will have PK samples drawn on Days 1-3 of Cycle 1. Please refer to Sections, 6.1.2.2 and 12.1 for details.

¹⁴ Correlative studies will only be done on the 6 patients in the PK cohort, as well as all patients enrolled to the phase II portion of the study.

¹⁵ Copy of pathology report is sufficient for registration. However a sample of tissue from a recent biopsy will be required for the 6 patients enrolled in the PK cohort and all patients in the phase II portion of the trial

¹⁶ Please refer to Section 12 for details regarding tissue requirements. Tissue from the most recent biopsy will be obtained for study purposes – patients will not undergo repeat biopsy for correlative studies. This applies to both PK cohort and Phase II patients

¹⁷ If baseline labs (chemistries, Mg, Phos, and CBC) were completed within 48 hours prior to start of treatment, they do not need to be repeated for Cycle 1 Day 1.

¹⁸ If serum chromogranin is completed within 14 days of treatment, it does not need to be repeated for Cycle 1 Day 1.

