9.3.1 Exploratory Study Statistical Analyses

9.3.1.1 MGMT expression

Changes in MGMT over time will be assessed using repeated measures analysis of variance; pre-treatment levels and changes in levels from baseline to day 30 will be related to response using a Wilcoxon rank sum test, and to PFS and OS using a proportional hazards regression model.

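### Section 9.3 censors patients removed for toxicity or preference at their last scan for 6-month PFS, so a later recorded death that Section 6.2.2.1.1 makes an event is dropped, and a later progression is handled ambiguously

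*Combined protocol and SAP*

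**What the plan says.** **Event.** Section 6.2.2.1.1: "PFS will be defined as the time from the first study treatment to the first occurrence of progression or death". Nothing is said about stopping treatment or about censoring.

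**Censoring.** Section 9.3 covers patients removed for reasons other than progression, naming toxicity and patient preference. They "will be censored for measurement of secondary endpoint, PFS at 6 months, at the time of their latest objective tumor assessment". The sentence refers back to earlier text, evidently the end of Section 9.1, which gives the same rule for phase I secondary endpoints. Neither section makes an exception for an event recorded later.

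**Data after treatment.**
- Deaths, Section 5.9: "After treatment discontinuation, patients will be followed every 6 months for 1 year in clinic and/or via phone for survival follow-up".
- Scans: the documents are mixed. Section 6.2.2.1 schedules imaging "after every 2 cycles of protocol therapy until study discontinuation". Table 10, footnote 12 says: "Patients removed from the study for disease progression who have no ongoing toxicity will undergo one last off-treatment visit for response". But Table 10 itself marks imaging in both follow-up columns, and Section 6.5, when discussing symptomatic deterioration, asks for efforts to document progression after treatment has stopped.

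**Estimation.** Section 9.2.2: "The proportion with PFS at 6 months will also be calculated based on RECIST criteria". No estimator is named. Section 9.3.1.1 relates MGMT "to PFS and OS using a proportional hazards regression model" and does not say which PFS rule applies. Section 2.2.2 lists PFS as a secondary objective without restricting it to its 6-month value.

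**The concern.** Take a patient removed for toxicity at month 2, last scanned at week 8, whose death at month 5 is recorded at survival follow-up. Under Section 6.2.2.1.1 this is a PFS event before 6 months. Under Section 9.3 the patient is censored at week 8 and the death never enters the estimate. Both cannot govern the same endpoint.

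The affected group is likely to exist. Section 5.8.2 requires removal for unacceptable toxicity, and Section 5.7.3 removes a phase II patient when either drug is stopped.

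Censoring of this kind gives the 6-month PFS of Section 6.2.2.1.1 only if removed patients go on to have the same risk as those who stay. If their risk is higher, the reported figure is too high; if lower, too low. What is at stake is one secondary endpoint and any analysis that borrows its rule.

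**Working it through.** **1. The plan's own figures.** No target, power or sample size rests on 6-month PFS, so there is nothing of that kind to reproduce. As background, the ORR design of Section 9.2.1 (stop at 2 or fewer of 11; 8 or more of 27 to succeed) gives by exact binomials a type I error of 0.099, power of 0.808 and early stopping probability of 0.651 at a 19% response rate. These agree with the stated 0.10, 80% and 65%. The PFS rule does not enter.

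**2. The two rules side by side, for a patient removed for toxicity or preference**

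| What happens after removal | Section 6.2.2.1.1 | Section 9.3 |
|---|---|---|
| Death after the last scan | Event | Censored at last scan |
| Progression on a post-removal scan | Event | Unclear: that scan may be the latest assessment, but the rule still says to censor |
| Neither recorded | No event | Censored at last scan |

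The rules clearly differ in the first row and may differ in the second.

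**3. Hand example (assumed counts).** Of 27 patients, 6 are removed without progression at the week-8 scan. Of the other 21, 7 have events between then and month 6. Censoring the 6 gives (21 - 7)/21 = 14/21 = 66.7%. Counting their later events, with the rest of the 6 followed event-free to month 6:

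- 0 of 6 have events: 20/27 = 74.1%
- 2 of 6: 18/27 = 66.7%, identical, because 2/6 equals 7/21
- 4 of 6: 16/27 = 59.3%

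The censoring rule can err in either direction, and is neutral at equal risk.

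**4. Weight of one death.** 26 patients were simulated with event hazard -ln(S6)/6 and removal hazard -ln(1 - w)/6, where S6 is 6-month PFS and w the proportion removed by month 6 absent progression. A 27th was either censored at week 8 or counted as dying at month 5. Counting the death lowers the mean Kaplan-Meier estimate at 6 months by:

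- S6 = 60%: 3.0 points (w = 15%) or 3.6 (w = 30%)
- S6 = 81%: 3.7 points (w = 15%) or 4.4 (w = 30%)

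**5. Bias of the Section 9.3 rule.** Inputs:

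- S6 of 60% (Section 1.3.2, sorafenib) or 81% (Section 1.4.1, pazopanib with octreotide), used only as a range.
- w of 15%, 30% or 55%. This trial's rate is not given; 55% is the toxicity discontinuation rate for temozolomide plus thalidomide in Section 1.5.3, a different regimen.
- Hazard multiplied by h after removal (assumed).
- Scans every 8 weeks; an event is detected at the next scan, or at death if sooner. Median survival after progression is 12 months (assumed; 6 and 24 months change little).

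Bias is the Kaplan-Meier estimate at 6 months under Section 9.3 minus the estimate with everyone scanned, in points (400,000 simulated patients per cell, simulation error about 0.1 to 0.2):

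| S6 | w | h = 0.5 | h = 1 | h = 1.5 | h = 3 |
|---|---|---|---|---|---|
| 60% | 30% | -2.5 | 0 | +2.0 | +6.3 |
| 60% | 55% | -5 | 0 | +3.8 | +12.5 |
| 81% | 30% | -1.3 | 0 | +1.1 | +4.1 |
| 81% | 55% | -2.5 | 0 | +2.2 | +8.2 |

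Values at w = 15% are smaller. Timing matters: if a fraction d of those event-free at month 2 all left then, the bias would be S(2) × d × [exp(-4λ) - exp(-4hλ)], with λ = -ln(S6)/6. For S6 = 60%, d = 0.55 and h = 3 this is 0.843 × 0.55 × (0.711 - 0.360) = 16.3 points.

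**6. Sampling error.** sqrt(S6(1 - S6)/27) = sqrt(0.60 × 0.40/27) = 9.4 points, or sqrt(0.81 × 0.19/27) = 7.5 points. Censoring would widen these somewhat.

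**7. Would rewording alone cure it?** If removed patients get no further scans, only deaths are added. At h = 3 and w = 30% the bias goes from +6.3 to +7.1 (60% base) and from +4.1 to +3.8 (81% base). With half of them scanned it falls to +3.3 and +1.7. At w = 55%, h = 3 and no scans, the 60% base worsens by up to about 1.5 points.

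**The case against.** **Section 9.3 may only supply the rule that Section 6.2.2.1.1 lacks, loosely worded and meant for patients without an event.** This is possible. The text does not say so, and read as written it censors every patient in the group.

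**Removal from study may mean that no further data exist.** For withdrawn consent this stands, and censoring at the last scan is then unavoidable. Elsewhere it does not: Sections 5.7.3 and 5.8.2 tie removal from study to stopping treatment, and Section 5.9 still follows patients for survival after treatment ends.

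**Censoring when treatment stops can be a legitimate choice.** It can, but it then estimates something other than the endpoint in Section 6.2.2.1.1. The plan neither says so nor provides the other analysis.

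**The practical effect may be small.** PFS has no test or target, the bias vanishes at equal risk, and many scenarios lie within sampling error. All of this stands, and it limits the point to a correction of wording.

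Three stronger readings are tempting but unsupported:
- A reader might infer that every later progression is discarded. The latest assessment is not limited to scans before removal, so that half is ambiguous; only deaths after the last scan are clearly lost.
- A reader might infer that 6-month PFS will be inflated. No document gives the removal rate or the later risk of removed patients.
- A reader might infer that progression is not sought after treatment. Table 10 and Section 6.5 point the other way, though neither guarantees scans.

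The missing estimator and the unstated rule for the MGMT model are separate gaps. They add no weight to the conflict, but the same edit can close them.

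**Conclusion.** The conflict is real and narrow. For patients removed for toxicity or preference, Section 9.3 drops a recorded death that Section 6.2.2.1.1 counts, and leaves a progression found after removal open to two readings. Two analysts could report different 6-month figures from the same data; one such death moves the estimate by about 3 to 4.4 points under the assumptions in step 4.

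The direction and size of bias cannot be known from the documents. In the staggered-removal model it runs from about -5 to +12.5 points and is about zero at equal risk. At 30% removed, every value is below the standard error of 7.5 to 9.4 points. At 55% removed and a hazard ratio of 3 it exceeds it (+12.5 against 9.4; +8.2 against 7.5), so it cannot be said in general to stay within sampling error. All these sizes rest on assumed removal rates and hazards.

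The ORR endpoint, the Simon rule and the sample size are unaffected. The point merits correction before the data are analysed because a stated rule contradicts the endpoint definition, not because a large bias has been shown.

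**What to change.** - In Section 9.3, state that every documented progression or death is a PFS event, on or off treatment; that patients with neither are censored at their last adequate tumour assessment; and that this holds for all PFS analyses, including the MGMT model.
- Align Section 9.1, so that the back-reference in Section 9.3 does not lead to a contrary rule.
- In Section 9.2.2, name Kaplan-Meier with a confidence interval for 6-month PFS.
- Keep the present Section 9.3 rule as a sensitivity analysis.
- Report how many removed patients had no off-treatment scan before death or last contact.

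**Cost.** Wording and one extra tabulation; no added visits or scans. The 6-month figure may be less favourable. Where off-treatment scans are not done, the new wording changes the bias little and can be slightly worse: about 1 point or less at 30% removed, up to about 1.5 points at 55% in this model. That is the reason for the count of unscanned patients. Events after withdrawal of consent may be unavailable; limiting the rule to documented events covers this.

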9.3.1 Exploratory Study Statistical Analyses

9.3.1.1 MGMT expression

Changes in MGMT over time will be assessed using repeated measures analysis of variance; pre-treatment levels and changes in levels from baseline to day 30 will be related to response using a Wilcoxon rank sum test, and to PFS and OS using a proportional hazards regression model.

9.4 Replacement Policy

A patient may be replaced if protocol therapy is discontinued due to early disease progression, defined as occurring within the first 28 days of therapy. Patients will not be replaced if taken off study due to toxicity, however, if a patient is taken off study during their DLT period for a reason unrelated to study treatment, another patient may be added to that cohort.

9.5 Statement of Feasibility

The Northwestern University GI Oncology program derives study patient populations from patients currently undergoing treatment or evaluation at the Robert H. Lurie Comprehensive Cancer Center (RHLCCC), as well as from a broad referral base in the Chicago and Midwest area. The weekly multidisciplinary GI Tumor Board at RHLCCC provides additional means to identify potential study subjects. Based upon these resources, we anticipate monthly accrual of approximately 2-3 patients with advanced PNET. Estimated time of study completion is 2.5 years. [name], the Principal Investigator of this proposal, has experience leading and designing clinical trials in GI oncology. She is also an active member of the ECOG GI committee. She has received an NCCN grant in the past for evaluating temsirolimus and sorafenib in HCC. As of June 2017, she is being replaced by [name] as Principal Investigator of this study. The co-investigators on this study proposal are all members of the RHLCCC with strong clinical research backgrounds in the development and implementation of clinical trials in gastrointestinal malignancies. [name] is the director of the GI oncology program and the chair of the ECOG Gastrointestinal and Data Monitoring Committees. The group includes well developed research infrastructure including research nurses and nurse practitioners, data managers, biostatisticians, and research pharmacists. Safety monitoring and oversight will be provided by the RHLCCC Data Monitoring Committee (DMC) in accordance with the [Data Safety Monitoring Plan \(DSMP\) of the RHLCCC](#). Additional details regarding how this study will be monitored can be referenced in Appendix IV.

10.0 ADVERSE EVENT MONITORING & REPORTING

This trial will be conducted in accordance with the DSMP of the RHLCCC (<http://cancer.northwestern.edu/CRO/data/Data andSafetyMonitoringPlanMay2014.pdf>). The level of risk attributed to this study requires High Intensity Monitoring, as outlined in the DSMP.

10.1 Adverse Event Monitoring

Collection and reporting of adverse event (AE) data is required as part of every clinical trial, and is done to ensure the safety of patients enrolled in this study as well as those who will enroll in future studies using similar agents. Toxicity will be assessed daily during treatment, and at least twice weekly (if not more frequently) after treatment until count recovery (as described in Section 7.0). All adverse events will be reported on the appropriate eCRF (as outlined in

Appendices V and VI). Additionally, certain serious adverse events (SAEs) will be reported in an expedited manner to allow for optimal monitoring of patient safety and care.

All patients experiencing an AE, regardless of its relationship to study drug, will be monitored until one of the following occurs:

- 10.1.1** The AE resolves or the symptoms or signs that constitute the AE return to baseline.
- 10.1.2** Any abnormal laboratory values have returned to baseline.
- 10.1.3** There is a satisfactory explanation other than the study drug for the changes observed.
- 10.1.4** Death.

10.2 Definitions & Descriptions

10.2.1 Adverse Event

An AE is any untoward medical occurrence in a patient receiving study treatment and which does not necessarily have a causal relationship with this treatment. An AE can therefore be any unfavorable and unintended sign (including an abnormal laboratory finding), symptom, or disease temporarily associated with the use of an experimental intervention, whether or not related to the intervention.

Recording of AEs should be done in a concise manner using standard, acceptable medical terms. In general, AEs are not procedures or measurements, but should reflect the reason for the procedure or the diagnosis based on the abnormal measurement. Preexisting conditions that worsen in severity or frequency during the study should also be recorded (a preexisting condition that does not worsen is not an AE). Further, a procedure or surgery is not an AE; rather, the event leading to the procedure or surgery is considered an AE.

If a specific medical diagnosis has been made, that diagnosis or syndrome should be recorded as the AE whenever possible. However, a complete description of the signs, symptoms and investigations which led to the diagnosis should be provided. For example, if clinically significant elevations of liver function tests are known to be secondary to hepatitis, “hepatitis” and not “elevated liver function tests” should be recorded. If the cause is not known, the abnormal test or finding should be recorded as an AE, using appropriate medical terminology (e/g/ thrombocytopenia, peripheral edema, QT prolongation).

10.2.2 Severity of AEs

All non-hematologic adverse events will be graded according to the NCI Common Terminology Criteria for Adverse Events (CTCAE) version 4.03. The CTCAE v4 is available at

<http://ctep.cancer.gov/reporting/ctc.html>

If no CTCAE grading is available, the severity of an AE is graded as follows:

- 10.2.2.1 Mild (grade 1):** the event causes discomfort without disruption of normal daily activities.
- 10.2.2.2 Moderate (grade 2):** the event causes discomfort that affects normal daily activities.
- 10.2.2.3 Severe (grade 3):** the event makes the patient unable to perform normal daily activities or significantly affects his/her clinical status.
- 10.2.2.4 Life-threatening (grade 4):** the patient was at risk of death at the time of the event.
- 10.2.2.5 Fatal (grade 5):** the event caused death.

10.2.3 Serious Adverse Event

An SAE is any untoward medical occurrence i.e. an undesirable sign or symptom or medical condition that at any dose results in one of the following outcomes:

- 10.2.3.1 Death:** if death results from progression of the disease, the disease progression should be reported as an SAE itself.
- 10.2.3.2 A life-threatening adverse event:** the patient was at risk of death at the time of the event (this does not refer to an event that hypothetically might have caused death if it were more severe).
- 10.2.3.3 A congenital anomaly/birth defect.**
- 10.2.3.4 A persistent or significant incapacity** or substantial disruption of the ability to conduct normal life functions.
- 10.2.3.5 An adverse event that requires inpatient hospitalization or prolongation of existing hospitalization for ≥ 24 hours,** unless hospitalization is for:
 - 10.2.3.5.1** Routine treatment or monitoring of the studied indication, not associated with any deterioration in condition (specify what this includes).
 - 10.2.3.5.2** Elective or pre-planned treatment for a pre-existing condition that is unrelated to the indication under study and has not worsened since the start of study drug.
 - 10.2.3.5.3** Treatment on an emergency outpatient basis for an event not fulfilling any of the definitions of a SAE given above and not resulting in hospital admission.
 - 10.2.3.5.4** Social reasons and respite care in the absence of any deterioration in the patient's general condition.
- 10.2.3.6 Is medically significant or is an important medical event,**

Important medical events are those that may not meet any of the above criteria, but that are clearly of major clinical significance in the judgment of the investigator. They may jeopardize the subject, and/or may require intervention to prevent one of the other serious outcomes noted above. Examples might include: allergic bronchospasm requiring intensive treatment in an emergency room or at home, convulsions that may not result in hospitalization, or development of drug abuse or drug dependency.

